### [Management of Cytopenias](#)

Myelosuppression and the related adverse events (thrombocytopenia, anemia, neutropenia, and febrile neutropenia) are common in both treated and untreated patients with AML. Subjects with baseline neutropenia or those who have significant bone marrow involvement may be particularly at high risk.

If a subject achieves CRi or has a morphologic leukemia free bone marrow (MLFS) (i.e., bone marrow blasts  $< 5\%$ ) after completion of Cycle 1, venetoclax should be interrupted to allow for ANC recovery from Day 29 until  $\text{ANC} \geq 500/\mu\text{L}$  or up to 14 days.

Cycle 2 administration of azacitidine or decitabine will also be delayed until  $\text{ANC} \geq 500/\mu\text{L}$ . Both venetoclax and azacitidine or decitabine will resume on the same day after the interruption. If a subject presents with new onset Grade 4 neutropenia for more than 1 week during subsequent cycles, unless it is thought to be due to the underlying disease, dosing with venetoclax and azacitidine or decitabine may be interrupted until  $\text{ANC} \geq 500/\mu\text{L}$ .

After Cycle 3, for subjects in CR/CRi who required interruption or delay of study drug administration for cytopenias (neutropenia [ $\leq 500/\mu\text{L}$ ] or thrombocytopenia [ $\leq 50 \times 10^3/\mu\text{L}$ ]) venetoclax should be administered for 21 days out of 28 days during each of the subsequent cycles. The treatment cycle should also be delayed to allow for count recovery until  $\text{ANC} \geq 500/\mu\text{L}$ , platelet count  $\geq 50 \times 10^3/\mu\text{L}$ , or for up to 14 days, whichever occurs earlier.

Subjects with resistant disease, based on modified IWG criteria (as described in the Operations Manual, Section 3.16) after Cycle 1 should receive subsequent cycles of study treatment with no dose interruption/delay until a repeat bone marrow assessment demonstrates CRi or MLFS. Transfuse blood products, administer prophylactics, and administer treatment anti-infectives as clinically indicated and as per institutional practice. Once CRi or MLFS is achieved, dose interruptions and reduction in duration of venetoclax administration for neutropenia should be implemented as described above, beginning from the cycle where a CRi or MLFS is demonstrated. If hematologic recovery (ANC or platelets) is achieved within 14 days after completion of the cycle (where the CRi or MLFS is demonstrated), the duration of venetoclax is reduced to 21 days of the subsequent 28-day cycle.

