#### Dose Modifications for Venetoclax

See [Appendix G](#) for dose modifications for toxicities related to venetoclax. Venetoclax dose modifications for possible drug-drug interactions are provided in the Section [5.4](#).

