## APPENDIX G. RECOMMENDED DOSE REDUCTIONS RELATED TO DRUG TOXICITIES IN AML

### Recommended Venetoclax Dose Modifications for Toxicities

Event	Occurrence	Action
Hematologic Toxicities		
Grade 4 neutropenia with or without fever or infection; or Grade 4 thrombocytopenia (see Warnings and Precautions in Management of Cytopenias, Section 6.2)	Occurrence prior to achieving remission	Transfuse blood products, administer prophylactic and treatment anti-infectives as clinically indicated. In most instances, venetoclax and azacitidine or decitabine cycles should not be interrupted due to cytopenias prior to achieving remission.
	First occurrence after achieving remission and lasting at least 7 days	Delay subsequent treatment cycle of venetoclax and azacitidine or decitabine and monitor blood counts. Administer granulocyte-colony stimulating factor (G-CSF) if clinically indicated for neutropenia. Once the toxicity has resolved to Grade 1 or 2, resume venetoclax therapy at the same dose in combination with azacitidine or decitabine or low-dose cytarabine.
	Subsequent occurrences in cycles after achieving remission and lasting 7 days or longer	Delay subsequent treatment cycle of venetoclax and azacitidine or decitabine and monitor blood counts. Administer G-CSF if clinically indicated for neutropenia. Once the toxicity has resolved to Grade 1 or 2, resume venetoclax therapy at the same dose and the duration reduced by 7 days for each subsequent cycle.

AML = acute myeloid leukemia; G-CSF = granulocyte-colony stimulating factor.

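### For a first Grade 4 neutropenia of at least 7 days in a subject in CR/CRi after Cycle 3, the protocol gives inconsistent rules for ending the treatment delay and does not say which governs

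*Protocol*

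**What the plan says.** Four places in the protocol bear on this subject.

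- **Section 6.2, Management of Cytopenias, paragraph on later cycles.** It opens "After Cycle 3, for subjects in CR/CRi who required interruption or delay of study drug administration for cytopenias" and continues that "venetoclax should be administered for 21 days out of 28 days during each of the subsequent cycles". It also delays the cycle until ANC is at least 500/µL and platelets at least 50 × 10³/µL, "or for up to 14 days, whichever occurs earlier". It does not separate first from later events.
- **Section 6.2, same subsection, preceding paragraph.** If Grade 4 neutropenia newly appears in a later cycle and persists beyond one week, and is not put down to the leukemia, dosing may be held until ANC reaches 500/µL. This is permissive and has no day limit.
- **Appendix G.** For "First occurrence after achieving remission and lasting at least 7 days", the next cycle is delayed. Then: "Once the toxicity has resolved to Grade 1 or 2, resume venetoclax therapy at the same dose in combination with azacitidine or decitabine". No day limit is given, and the number of venetoclax days is not mentioned. Only the row for later occurrences adds a shortening: "resume venetoclax therapy at the same dose and the duration reduced by 7 days for each subsequent cycle".
- **Section 6.1, Adverse Events of Special Interest.** If ANC is not back to 500/µL by 14 days of interruption, or a longer break between cycles is needed, a marrow aspirate is optional before the next cycle starts.

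The texts refer to each other. Section 6.2 (Dose Modifications for Venetoclax) points to Appendix G "for dose modifications for toxicities related to venetoclax", and Appendix G points back: "see Warnings and Precautions in Management of Cytopenias, Section 6.2". Neither says which prevails.

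**The concern.** The rules meet in one subject. Appendix G tells the site to delay the next cycle. A subject so delayed has then required a delay for cytopenia, which is the condition in the later-cycles paragraph of Section 6.2. Following one text therefore brings the other into play, and the two end the delay differently.

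The stake is patient safety: a subject in remission whose ANC is still in Grade 4 at day 14 may be restarted at one site and kept off treatment at another. About 60 subjects are planned at about 20 sites, so consistent dosing depends on the text being clear. A site that follows one text may also be departing from the other, although Section 5.9 forbids intentional deviations. A lesser effect falls on the exposure, interruption and dose-intensity summaries in SAP 8.2.

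**Working it through.** The plan states no figure to reproduce. The check sets the rules side by side and applies them to the same subject.

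**Restart rule.** SAP 9.4 puts Grade 4 neutropenia at ANC below 0.5 × 10⁹/L, which is 500/µL. Take ANC 400/µL on day 14 of the delay.

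| Text | What ends the delay | Day limit | Day 14, ANC 400/µL |
|---|---|---|---|
| (a) 6.2, later-cycles paragraph | ANC ≥ 500/µL with platelets ≥ 50 × 10³/µL | 14 days | ends, if read alone |
| (b) 6.2, new Grade 4 neutropenia beyond a week | ANC ≥ 500/µL | none | may continue |
| (c) Appendix G, first occurrence | Grade 1 or 2 | none | continues |
| (d) 6.1, optional marrow | sets no rule | treats longer breaks as possible | day 14 not a firm end |

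This comparison needs no outside figure.

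There is probably a difference in the count level as well. An ANC of 500/µL has only just left Grade 4. The documents print no limits for Grades 1 to 3, so the upper limit of Grade 3 is an assumption here, varied over 750, 1,000 and 1,500/µL. At ANC 500 or 600/µL on day 5, with platelets recovered, (a) ends the delay, while (c) continues it under all three assumed limits. This part is an inference. No conflict on the platelet level is claimed.

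**Other time limits.** Neither of the following sets a restart day for this subject.

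- Section 5.5 lists an interruption of more than 4 weeks as a reason for withdrawal, but only when there is no clinical benefit. This subject is in remission.
- Section 6.1 requires discussion of delays over 21 days, but directly after a sentence on events unrelated to study treatment.

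**Venetoclax days (secondary, by inference).** Inputs are six 28-day cycles (Section 4.1), 21 of 28 days (Section 6.2) and 28 − 7 = 21 days (Appendix G, later occurrences). Assume all planned days are dosed, there is one qualifying event, and the first-occurrence row means an unshortened cycle.

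- Full schedule: 6 × 28 = 168 days.
- Event in Cycle 4, Cycle 5 delayed: under 6.2, 4 × 28 + 2 × 21 = 154; under Appendix G, 168. The difference is 14 days.
- Event in Cycle 5, Cycle 6 delayed: under 6.2, 5 × 28 + 21 = 161; under Appendix G, 168. The difference is 7 days.

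The difference is therefore 7 days per remaining cycle. If Section 6.2 fills the silence in the first-occurrence row, both texts give 154 or 161 and the difference is 0. It may also be 0 if the 6.2 paragraph concerns only subjects with earlier delays.

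The scope of the 6.2 paragraph matters for a delay before the end of Cycle 3 too. If the delay itself must fall after Cycle 3, the total is 168 days. If the words fix only when the shorter schedule starts, it is 3 × 28 + 3 × 21 = 147.

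**The case against.** The best defence is that these texts are guidance with room for judgement and are meant to be read together. Appendix G is headed as recommendations, Section 6.2 uses permissive or advisory verbs, and the medical monitor can be consulted. Section 6.1 openly foresees ANC that has not recovered by day 14. The azacitidine dose table in Section 6.2 (Table 3) has a column for recovery beyond 21 days. A site is thus not left with only two opposed instructions.

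Much of this stands, and it rules out two stronger readings that a reader might infer.

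- **That Section 6.2 forces a restart at day 14 whatever the count.** Only one of its paragraphs, read alone, ends the delay then. Another permits interruption without a day limit, and Section 6.1 does not treat day 14 as a firm end.
- **That the protocol plainly prescribes 21 venetoclax days in one place and 28 in another.** Appendix G's first-occurrence row does not state a number of days. An unshortened cycle is the natural reading, because only the next row takes off 7 days, but it comes from silence, and other readings give no difference.

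The defence does not remove the inconsistency in the restart rule. The extra sentences add further rules and rank none of them. Nor does the more specific text settle it: Appendix G is narrower by event, and the Section 6.2 paragraph is narrower by timing and remission status.

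**Conclusion.** The inconsistency in the restart rule holds for the case described: CR/CRi, after Cycle 3, first Grade 4 neutropenia of at least 7 days. At day 14 with ANC below 500/µL, the protocol can be followed to three different results: end the delay, permit it to continue, or continue it. This rests on the printed text and on the SAP's Grade 4 limit alone.

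The difference in venetoclax days is secondary and inferred: 7 days per remaining cycle on the natural reading, and possibly 0 on others. It should not be quoted as an established loss of exposure.

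A reader might also infer that the primary result is compromised. The documents do not support that: these subjects are already in CR/CRi when the rules diverge, so the CR + CRi rate is largely unaffected. The documents do not show how many subjects would meet this case, and variation between sites is a risk rather than something shown. The point should be corrected because it bears on patient safety and the correction is cheap.

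**What to change.** The sponsor's medical team should reconcile the cytopenia paragraphs of Section 6.2 (including the one on disease initially resistant after Cycle 1, whose overlap with Appendix G is unclear), the ANC recovery sentence in Section 6.1, and Appendix G. The result should:

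1. give one rule for ending the delay, including what applies at day 14 without recovery;
2. give one rule for venetoclax days per cycle, saying whether a first occurrence in Appendix G leaves the number of days unchanged;
3. state whether the Cycle 3 condition in Section 6.2 refers to when the delay occurs or to when the shorter schedule starts;
4. state which text governs if any difference remains.

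This review takes no view on which clinical rule is right.

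Two clerical corrections are separate and can be made at the same time. Section 6.2 sends the reader to Appendix G for TLS, but that appendix lists only hematologic toxicities. Appendix G also names low-dose cytarabine, which is not a study drug here.

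The cost is a clarifying amendment or a letter to sites. No new data are needed.

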## Azacitidine

During subsequent cycles, if hematologic recovery with > 25% increase above the nadir is not seen by Day 28, reassess counts every 7 days. If a 25% increase has not been achieved within 14 days after the completion of a cycle, based on the bone marrow biopsy cellularity, azacitidine dose adjustment can be made per [Table 3](#), or according to institutional standards.

**Table 3. Azacitidine Dose Modification**

Bone Marrow Cellularity	% Dose in the Next Cycle if Recovery is Not Achieved Within 14 Days	
	Recovery ≤ 21 days	Recovery > 21 days
15 – 50%	100%	50%
< 15%	100%	33%

## Decitabine

If a dose reduction for decitabine is believed to be necessary, a discussion with the AbbVie medical monitor is required.

### Management of Non-TLS Serum Electrolytes and Renal Impairment

If unexplained reductions in serum bicarbonate levels to < 20 mEq/L occur, azacitidine dosage should be reduced by 50% on the next course. Similarly, if unexplained elevations of blood urea nitrogen (BUN) or serum creatinine occur, the next cycle should be delayed until values return to normal or baseline and the dose should be reduced by 50% on the next treatment course.

### Management of Decrease in Spermatogenesis

Venetoclax may cause a decrease in spermatogenesis. Male subjects considering preservation of fertility should bank sperm before initiating treatment with venetoclax.

### Management of Other Toxicities

If other events occur that are related to venetoclax, azacitidine, or decitabine, the investigator, in consultation with the AbbVie medical monitor, may interrupt or reduce the dose of venetoclax and/or azacitidine or decitabine, as appropriate. Grade 3 or greater nonhematologic toxicity (e.g., nausea, vomiting, and diarrhea when additional supportive care fails or neurotoxicity, AST, ALT, or bilirubin increased), that is related to venetoclax, azacitidine, or decitabine will require interruption and possible discontinuation of dosing. Venetoclax, azacitidine, or decitabine may be reintroduced, but only at a reduced dose, (in consultation with the AbbVie medical monitor) if the toxicity returns to ≤ Grade 1 or to baseline if Grade 2 at study entry.

### Management of Infections

Anti-infective prophylaxis should be implemented per regional guidelines or institutional standards including appropriate prophylaxis for bacterial, viral and fungal infections. Potential for drug-drug interactions should be considered.

All subjects should be monitored for new onset hematologic toxicity and renal toxicities, with dose delay or reduction as appropriate. Please follow local, approved product label or applicable Summary of Product Characteristics (SmPC) for monitoring guidelines.

#### Dose Modifications Based on Toxicities

Subjects who discontinue 1 study drug because of study drug-related toxicities may continue to receive the other study drug for up to a maximum of 21 days, as determined by the investigator.

#### Dose Modifications for Venetoclax

See [Appendix G](#) for dose modifications for toxicities related to venetoclax. Venetoclax dose modifications for possible drug-drug interactions are provided in the Section [5.4](#).

## 7 STATISTICAL METHODS & DETERMINATION OF SAMPLE SIZE

### 7.1 Statistical and Analytical Plans

---

Complete and specific details of the statistical analysis will be described and fully documented in the Statistical Analysis Plan (SAP). The SAP will be finalized prior to the database lock. The statistical analyses will be performed using SAS (SAS Institute Inc., Cary, North Carolina, USA).

### 7.2 Definition for Analysis Populations

---

Effectiveness and safety analyses will be performed on all subjects who receive at least one dose of venetoclax and azacitidine or decitabine. Subjects in the trial will have AML, will be treatment-naïve, and will be ineligible for intensive chemotherapy.

### 7.3 Statistical Analyses for Effectiveness

---

#### Endpoints

The primary objective for the study is to determine the composite complete remission rate (CR + CRi), during the initial 6 cycles of treatment, in AML subjects treated with venetoclax and either azacitidine or decitabine in an outpatient setting. The composite complete remission rate will be achieved if IWG criteria for complete remission or complete remission with incomplete hematologic recovery (CR + CRi) have been met.

Secondary effectiveness endpoints include:

- Overall Response (CR, CRi).
- RBC and platelet transfusion independence.

Exploratory effectiveness endpoints include:

- Time to blood count improvements and duration of blood count improvements
- Remissions (CR/CRi) in molecular subtypes.

Details on the primary and other effectiveness analyses are provided in the SAP.

#### Sample Size Estimation

The planned study will enroll approximately 60 subjects. A sample size of 60 subjects would ensure that the true CR + CRi rate will be within 13% of the observed CR + CRi rate with 95% confidence.

### 7.4 Statistical Analyses for Safety

---

The safety of venetoclax in combination with azacitidine or decitabine will be assessed by evaluation of study drug exposure, adverse events, serious adverse events, and deaths, as well as changes in laboratory and vital sign parameters.

Safety and tolerability will be assessed for all treated subjects and for azacitidine or decitabine separately.

Details on the statistical analyses for safety will be provided in the SAP.

## 8 ETHICS

### 8.1 Independent Ethics Committee/Institutional Review Board (IEC/IRB)

---

The Protocol, informed consent form(s), recruitment materials, and all subject materials will be submitted to the IEC/IRB for review and approval. Approval of both the Protocol and the informed consent form(s) must be obtained before any subject is enrolled. Any amendment to the Protocol will require review and approval by the IEC/IRB before the changes are implemented to the study. In addition, all changes to the consent form(s) will be IEC/IRB approved.

### 8.2 Ethical Conduct of the Study

---

The study will be conducted in accordance with the Protocol, Operations Manual, International Council for Harmonisation (ICH) guidelines, applicable regulations, and guidelines governing clinical study conduct and the ethical principles that have their origin in the Declaration of Helsinki. Responsibilities of the investigator are specified in [Appendix B](#).

In the event a significant disaster/crisis (e.g., epidemic/pandemic, natural disaster, conflict/combat) occurs leading to difficulties in performing protocol-specified procedures, AbbVie may engage with study site personnel in efforts to ensure the safety of subjects, maintain protocol compliance, and minimize risks to the integrity of the study while trying to best manage subject continuity of care. This

may include alternative methods for assessments (e.g., phone contacts or virtual site visits), alternative locations for data collection (e.g., use of a local lab instead of a central lab), and shipping investigational product and/or supplies direct to subjects to ensure continuity of treatment where allowed. In all cases, these alternative measures must be allowed by local regulations and permitted by IRB/IEC.

### **8.3 Subject Confidentiality**

---

To protect subjects' confidentiality, all subjects and their associated samples will be assigned numerical study identifiers or "codes." No identifiable information will be provided to AbbVie.

## **9 SOURCE DOCUMENTS AND CASE REPORT FORM COMPLETION**

The investigator is responsible for ensuring the accuracy, completeness, legibility, and timeliness of the data reported. All source documents should be attributable, legible, contemporaneous, original, accurate, and complete to ensure accurate interpretation of data. Clinical site monitoring is conducted to ensure that the rights and well-being of human subjects are protected, that the reported trial data are accurate, complete, and verifiable, and that the conduct of the trial is in compliance with the currently approved Protocol, ICH Good Clinical Practice (GCP), and applicable local regulatory requirement(s). During the COVID-19 pandemic, remote monitoring of data may be employed if allowed by the local regulatory authority, IRB/IEC, and the study site.

## **10 DATA QUALITY ASSURANCE**

AbbVie will ensure that the clinical trial is conducted with a quality management system that will define quality tolerance limits in order to ensure human subject protection and reliability of study results. Data will be generated, documented, and reported in compliance with the Protocol, ICH GCP, and applicable regulatory requirements.

## **11 COMPLETION OF THE STUDY**

The end-of-study is defined as the date of the last subject's last visit or date of the last follow-up contact, whichever is later.

## APPENDIX A. STUDY SPECIFIC ABBREVIATIONS AND TERMS

Abbreviation	Definition
ALT	alanine aminotransferase
AML	acute myeloid leukemia
ANC	absolute neutrophil count
AST	aspartate aminotransferase
BCL	B cell lymphoma
BCL-w	B-cell lymphoma - Walter and Eliza Hall Institute
CL/F	Apparent clearance
CLL	chronic lymphocytic leukemia
COVID-19	Coronavirus Disease – 2019
CR	complete remission
CRF	Case Report Form
CRh	complete remission with partial hematologic recovery
CRi	complete remission with incomplete blood count recovery
CS	clinically significant
CTCAE	Common Terminology Criteria for Adverse Events
CYP3A	cytochrome P450 3A isoform subfamily
ECG	Electrocardiogram
ECOG	Eastern Cooperative Oncology Group
eCRF	electronic case report form
FSH	follicle-stimulating hormone
GCP	Good clinical practice
ICH	International Council for Harmonisation of Technical Requirements for Pharmaceuticals for Human Use
IEC	Independent ethics committee
IMP	Investigational medicinal product
IRB	Institutional review board
IRT	Interactive response technology
IUD	intrauterine device
IUS	Intrauterine hormone-releasing system
IV	intravenous
IWG	International Working Group

MDS	myelodysplastic syndrome
MedDRA	Medical Dictionary for Regulatory Activities
MILFS	morphologic leukemia free bone marrow
NCI	National Cancer Institute
NCS	not clinically significant
P-gp	P-glycoprotein
PT	Preferred term
QD	once daily
RBC	red blood cell
RSI	Reference Safety Information
SAP	Statistical analysis plan
SC	subcutaneous(ly)
SOC	System organ class
SUSAR	Suspected unexpected serious adverse reaction
TLS	tumor lysis syndrome
ULN	upper limit of normal
US	United States
WBC	white blood cell
WHO	World Health Organization

